1.2.2 Clinical Summary

As of the data cutoff date of 1 February 2019, a total of 55 postmenopausal women with locally advanced or metastatic ER-positive (HER2-negative) breast cancer, including 29 patients in single-agent dose escalation, 6 patients in palbociclib-combination dose escalation, and 20 patients in single-agent dose expansion, had received at least one dose of GDC-9545 in Study GO39932. During dose escalation, 4 single-agent cohorts of 3 patients each were enrolled at 10-, 30-, 90-, and 250-mg doses, given once daily. To acquire additional PK, pharmacodynamic (PD), and safety data, up to 7 additional patients were enrolled to backfill single-agent dose-escalation cohorts at 10-, 30-, and 90-mg doses. The single-agent dose escalation completed enrollment in October 2018. No dose limiting toxicities (DLTs), related serious adverse events, or adverse events of special interest were reported. The MTD was not determined. Two dose levels of GDC-9545 were chosen for the single-agent dose expansion, 100 and 250 mg \pm LHRH agonist, and an escalation cohort combining 100 mg GDC-9545 with 125 mg palbociclib was enrolled.

GDC-9545 is tolerated well at all dose levels. The most frequently reported adverse events related to GDC-9545 in $\geq 10\%$ of patients were fatigue (15%), diarrhea and nausea (13%), and arthralgia (11%). Grade ≥ 3 adverse events were reported in 10 patients (18%), but all were considered unrelated to GDC-9545 by the investigators. Two patients have experienced serious adverse events considered not related to GDC-9545 by the investigator.

In Study GO39932, GDC-9545 was rapidly absorbed with peak concentrations achieved at 1–4 hours (mean time to maximum concentration) after single dose as well as at steady state. The geometric mean half-life after single dose ranged from 26.2–41.4 hours, indicating that once-daily dosing is appropriate for GDC-9545. In general, plasma exposures of GDC-9545 increased with doses at 10, 30, 90, and 250 mg after single and multiple doses. The expansion cohort's exposure was in line with escalation cohort exposure. Pharmacodynamics was assessed by functional imaging with [^{18}F]-fluoroestradiol-positron emission tomography and showed robust ER-target engagement across all doses.

Refer to the GDC-9545 Investigator's Brochure for details on nonclinical and clinical studies.

1.3 **STUDY RATIONALE AND BENEFIT–RISK ASSESSMENT**

GDC-9545 is a potent, orally bioavailable ER- α antagonist and inducer of ER- α degradation that competes with estrogens for binding to the ER with low nanomolar potency; it is being developed for the treatment of women with ER-positive breast cancer.

GDC-9545 demonstrated robust nonclinical activity in ER-positive breast cancer models of *ESR1*-wildtype and *ESR1*-mutation bearing disease. As described in Section 1.2.1.2, GDC-9545 was tolerated in safety pharmacology studies. Specific eligibility criteria

GDC-9545—Genentech, Inc.
22/Protocol GO40987, Version 4

designed to minimize potential risks are included in Section 4.1, and robust safety monitoring and risk mitigation strategies for all expected or potential safety risks are described in Section 5. The implementation of appropriate dose-modification and treatment guidelines, appropriate choice of inclusion/exclusion criteria, real-time safety monitoring and assessments, and periodic assessment of aggregate safety data and benefit–risk ratio combine to form the monitoring and risk mitigation system.

A window of opportunity (“window”) study is a type of neoadjuvant study where women with newly diagnosed hormone receptor-positive breast cancer are treated with an experimental drug for 2 weeks prior to surgery. These studies provide access to tumor tissue before, during, and after treatment for PD and correlative studies, providing critical insight into the optimal patient population, differences in activity and mechanisms between agents, influence of the tumor biology on sensitivity, and molecular mechanisms of response or resistance. Window studies are becoming the standard in developing a new drug in hormone receptor–positive breast cancer to inform dose selection and provide early readout on biologic activity.

To ensure consistency with current therapeutic standards, this study requires that definitive surgery take place 15 days (± 2 days) after the start of the study treatment. As such, a patient’s participation in this study is not expected to delay surgery beyond the standard waiting period. Furthermore, there is no nonclinical, clinical, or mechanistic evidence to suggest that GDC-9545 has a relevant impact on operability or that it increases risks associated with surgery.

Detailed studies in the neoadjuvant setting in prospective randomized clinical trials have demonstrated the utility and validity of changes in Ki67 as a predictor of benefit from of endocrine therapy treatment and of long-term outcome (Dowsett et al. 2005a; Dowsett et al. 2005b; Polychronis et al. 2005; Dowsett et al. 2006; Dowsett et al. 2007; Smith et al. 2007; Ellis et al. 2008; Baselga et al. 2009; Jones et al. 2009) (see Section 3.3.4.1 for additional details).

Although Ki67 measurements in preoperative trials cannot replace the need for adjuvant trials with clinical endpoints, when used along with additional PD data and Phase I dose escalation/expansion safety and efficacy data, they can be highly instructive in selecting the optimal dose for Phase III studies and defining the most appropriate patient populations.

As of November 2018, GDC-9545 has been well-tolerated and shown evidence of activity including in those patients with *ESR1* mutations (see Section 1.2.2). At all doses tested, patients with [¹⁸F]-fluoroestradiol positron emission tomography imaging have shown near-complete or complete responses. In addition, there is early indication of ER-pathway reduction by PD markers in the few on-treatment biopsies obtained from the Phase I study.

Overall, there is strong rationale to run a window of opportunity study to select the optimal dose of GDC-9545. In addition, GDC-9545 has a tolerable safety profile that poses minimal risk for patients during treatment and for surgery.

2. OBJECTIVES AND ENDPOINTS

This study will evaluate the pharmacodynamics, pharmacokinetics, safety and biologic activity of GDC-9545 in patients with Stage I–III operable ER-positive (HER2-negative) untreated breast cancer. Specific objectives and corresponding endpoints for the study are outlined below.

2.1 SAFETY OBJECTIVE

The safety objective for this study is to evaluate the safety and tolerability of GDC-9545 when administered in this patient population:

- Incidence and severity of adverse events, with severity determined according to NCI CTCAE v.5.0
- Change from baseline in targeted vital signs
- Change from baseline in targeted clinical laboratory test results, including ECGs

2.2 PHARMACOKINETIC OBJECTIVES

The PK objective for this study is to evaluate the GDC-9545 PK profile on the basis of the following endpoint:

- Plasma concentration of GDC-9545 at steady state

2.3 ACTIVITY OBJECTIVE

The activity objective for this study is to make a preliminary assessment of the activity of GDC-9545 on the basis of the following endpoint:

- Change from baseline in tumor cell proliferation measured by Ki67 expression between pre- and post-treatment samples

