The POETIC trial, a Phase III randomized clinical trial with approximately 4000 patients with early breast cancer, prospectively tested whether short-term perioperative endocrine therapy with an AI followed by standard adjuvant therapy can improve outcome in postmenopausal women with ER-positive breast cancer, whether the proliferation marker Ki67 as measured by immunohistochemistry after 2 weeks of AI therapy will predict for recurrence-free survival and whether molecular profiling 2 weeks after starting endocrine therapy predicts better for long-term outcome than at diagnosis. Similar to the IMPACT study, an early evaluation of Ki67 levels after 2 weeks of

treatment were shown to correlate to 5-year recurrence rate (low Ki67 8.5% 5-year TTR, high Ki67 19.6% 5-year TTR) (Robertson et al. 2018).

The neoadjuvant NEWEST study helped establish the optimal dose of the ER antagonist fulvestrant (500 mg) on the basis of significantly greater suppression of Ki67 compared with the lower dose of 250 mg after 4 weeks of treatment ($p < 0.0001$) (Kuter et al. 2012). Fulvestrant at 500 mg had a mean percent change from baseline of 78% at 4 weeks and 77% at 16 weeks. Fulvestrant at 250 mg had a mean percent change from baseline of 47% at 4 weeks and 63% at 16 weeks. These early Ki67 differences mirrored the results of the Phase III CONFIRM trial in advanced breast cancer, which also showed superiority of the 500-mg dose over the 250-mg dose (CBR in patients with measurable disease 45.6% versus 39.6% and PFS 6.5 months versus 5.4 months) (Di Leo et al. 2010).

In summary, reduction in Ki67 after neoadjuvant treatment with AIs and fulvestrant is a good marker of suppression of cellular proliferation, correlates with long-term efficacy outcomes, and mirrors results of large adjuvant or metastatic endocrine trials, which make it an attractive endpoint to assess in the present trial.

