6.1 DETERMINATION OF SAMPLE SIZE

This study is intended to obtain preliminary safety, PK, PD, and activity information. The sample sizes do not reflect any explicit power and type I error considerations.

The range of mean Ki67 expression changes are from 66% (Opportune) to 76% (IMPACT) for 2-week treatment (see Section 3.3.4.1). The planned enrollment for this study is approximately 75 patients. *At least 15 patients per cohort will provide a more robust safety profile as well as sample size for preliminary assessment of activity based on Ki67 expression. In Table 4, two-sided 80% CIs for Ki67 expression changes are listed, based on different assumed observed changes. The CIs show clear shift pattern at the sample size of 15 patients. To better evaluate the Ki67 expression change at 30 mg, the sample size is increased to 45. The 80% CIs show clear separation at this patient sample size.*

Table 4 Two-Sided 80% Confidence Intervals for Ki67 Expression Change

Sample size	Assumed Observed Change			
	60%	70%	80%	90%
15	(53.9%, 66.8%)	(62.9%, 77.9%)	(71.9%, 89.0%)	(80.9%, 100%)
20	(54.7%, 65.8%)	63.8%, 76.8%)	(72.9%, 87.8%)	(82.0%, 98.7%)
45	(56.4%, 63.8%)	(65.8%, 74.5%)	(75.2%, 85.1%)	(84.6%, 95.7%)

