6.6 ACTIVITY ANALYSES

The activity analysis population will consist of all patients who completed study treatment and who have tumor biopsy specimens available at baseline and at surgery for assessment of activity.

The activity is defined as change from baseline in tumor cell proliferation measured by Ki67 expression between pre- and post-treatment samples. The activity will be summarized by dose level.

On the assumption of a log normal distribution, Ki67 values will be log transformed before analysis. $\log(\text{Ki67}_{\text{post}})$ and $\log(\text{Ki67}_{\text{pre}})$ will be used to denote the mean of the logs of the post-treatment and pre-treatment values, respectively. A value of 0.1 will be added to every untransformed Ki67 value to avoid the mathematical anomaly that arises because the log of zero is minus infinity. The result of mean log changes and CI can be calculated and displayed on their original scale by back transformation.

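### Section 6.6 summarises the log change in Ki67 by dose without adjusting for baseline Ki67, which leaves avoidable noise in the comparison of doses

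*Combined protocol and SAP*

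**What the plan says.** Section 2.3 gives one endpoint for activity: "Change from baseline in tumor cell proliferation measured by Ki67 expression between pre- and post-treatment samples". Section 6.6 repeats it ("The activity is defined as change from baseline in tumor cell proliferation measured by Ki67 expression") and sets the scale: "On the assumption of a log normal distribution, Ki67 values will be log transformed before analysis", and "A value of 0.1 will be added to every untransformed Ki67 value" so that zeros can be logged. The mean log change and its CI are then back-transformed. On comparison between doses, section 6.6 says only this: "The activity will be summarized by dose level". It names no baseline covariate and no model across doses. Baseline Ki67 is not among the characteristics listed in section 6.3, although that list is open.

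Section 4.2 stratifies assignment by tumor grade (1 and 2 against 3) and nodal status. Section 4.1.1 sets no entry limit on Ki67. Section 6.1 plans 45 patients at 30 mg out of about 75, with at least 15 per cohort, so about 15 each at 10 mg and 100 mg. Section 3.3.2 says that the study's endpoints are biomarkers meant to define dose-PD and dose-activity relationships and to help choose the recommended Phase II dose.

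**The concern.** The purpose in section 3.3.2 requires the doses to be read against each other, even though section 6.6 describes each separately. Two cohorts given equally active doses can show different mean log changes if their baseline Ki67 differs and post-treatment Ki67 does not move in full proportion to baseline. Stratifying on two-level grade may reduce a Ki67 imbalance but cannot be relied on to remove it, least of all with 15 patients in a cohort. Baseline Ki67 is measured in every patient in the activity population, so the information that would remove this noise is already in hand and unused. At stake is precision in a small dose comparison. The validity of the endpoint is not in question.

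**Working it through.** **1. What the plan's own figures supply.** Table 4 is the only calculation for this endpoint: "two-sided 80% CIs for Ki67 expression changes are listed, based on different assumed observed changes". Its limits are change × exp(±z × SD/√n) with z = 1.2816, capped at 100%. One unstated SD of 0.3235 reproduces all 24 limits. For 60% at n = 15: 1.2816 × 0.3235/√15 = 0.107, and 60 × exp(∓0.107) gives 53.9 and 66.8, as printed. That SD belongs to the log of the percent change. It is not the SD of log baseline or of the log post/pre ratio, so the inputs below have to be assumed.

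**2. What the log ratio already removes.** A 70% fall from baselines of 10, 20 and 30 gives log changes, with the +0.1 rule, of log(3.1/10.1) = −1.18, log(6.1/20.1) = −1.19 and log(9.1/30.1) = −1.20. Proportional differences in baseline cancel almost exactly.

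**3. What remains.** Write log post = a(dose) + b × log pre + error, with SD s for log pre and residual SD τ. The log change then contains −(1−b) × log pre, so a contrast between two doses in mean log change carries (1−b) times the difference in mean log baseline. This is zero if b = 1. If b < 1, the cohort with the higher baseline shows the larger reduction.

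**4. Assumed ranges.** s = 0.6–1.0, b = 0.4–0.8, τ = 0.7–0.9. The documents give none of these.

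**5. Chance imbalance of one SE**, ignoring stratification: s × √(1/n₁ + 1/n₂).
- 15 against 15: √(2/15) = 0.365, so 0.219–0.365, a ratio of geometric mean baselines of 1.24–1.44.
- 15 against 45: √(1/15 + 1/45) = 0.298, so 0.179–0.298, a ratio of 1.20–1.35.

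**6. Carried into the change contrast**, (1−b) × SE, for 15 against 15: from 0.2 × 0.219 = 0.04 to 0.6 × 0.365 = 0.22. At the midpoints (s = 0.8, b = 0.6): 0.4 × 0.8 × 0.365 = 0.12.

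**7. Variance of the unadjusted contrast relative to the adjusted one**, 1 + (1−b)² s²/τ². The cohort sizes cancel.

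| b | s | τ | ratio |
|---|---|---|---|
| 0.8 | 0.6 | 0.9 | 1 + 0.04 × 0.36/0.81 = 1.02 |
| 0.6 | 0.8 | 0.8 | 1 + 0.16 × 0.64/0.64 = 1.16 |
| 0.4 | 1.0 | 0.7 | 1 + 0.36 × 1.00/0.49 = 1.73 |

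At the midpoints the SE is √1.16 = 1.08 times as large. The formula treats the slope as known. Estimating it costs one of about 75 − 3 = 72 residual degrees of freedom, so the 1.02 end is in practice no gain.

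**8. On the reported scale.** A shift of 0.12 moves a 76% reduction to 1 − 0.24 × exp(0.12) = 72.9% or to 1 − 0.24 × exp(−0.12) = 78.7%. Only one of these can occur in a given trial, so the effect is about 3 points. For comparison, at the midpoints the SD of an individual log change is √(0.16 × 0.64 + 0.64) = 0.86. The 80% CI around 76% at n = 15 is then 1 − 0.24 × exp(±1.2816 × 0.86/√15), about 68% to 82%.

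**The case against.** The strongest reply is that this is a descriptive Phase I study. Section 6.1 states: "The sample sizes do not reflect any explicit power and type I error considerations". Section 2.3 calls the assessment preliminary, and section 1.3 says that Ki67 is to be read with other PD data and with Phase I safety and efficacy data. No ranking of doses is specified. A chance imbalance is also ordinary sampling error: it is already part of the spread of individual log changes, and so of the CI that section 6.6 produces. All of this stands. It limits the point to a gain in precision. It does not remove it, because section 3.3.2 still gives the endpoint a comparative purpose.

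The protocol also supports change as a measure. Section 1.3 cites changes in Ki67 as a predictor of benefit and long-term outcome. In section 3.3.4.1, short-term change correlated with recurrence-free survival in IMPACT, and percent change separated two fulvestrant doses in NEWEST (78% against 47% at 4 weeks), the closest precedent for this trial's aim.

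A reader might nevertheless infer that the on-treatment level should replace change, because section 3.3.4.1 says of the POETIC trial of about 4000 patients that Ki67 levels after 2 weeks of "treatment were shown to correlate to 5-year recurrence rate (low Ki67 8.5% 5-year TTR, high Ki67 19.6% 5-year TTR". Those figures show that level is prognostic. They do not show that it compares doses better. In the model above, an unadjusted level carries b of a baseline imbalance and change carries 1 − b: 0.6 against 0.4 at b = 0.6, and 0.8 against 0.2 at b = 0.8. Whenever b exceeds 0.5, an unadjusted level is the more exposed of the two. The documents also give no low-Ki67 cut-off.

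**Conclusion.** The point holds as an inexpensive improvement in precision. The dose summaries in section 6.6 leave baseline Ki67 unused, and if the slope is below 1 the dose contrasts are noisier than they need be: 1.02 to 1.73 times the adjusted variance over the assumed ranges, about 1.16 at the midpoints, and no gain if the slope is 1. The SDs and slope are assumptions, and stratification by grade, which the calculation ignores, may make the gain smaller.

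Two stronger readings are not supported. One is that the plan compares untransformed changes; it uses a log ratio, which removes proportional differences. The other is that the dose ranking is biased by about 6 points, which a reader might infer by taking 72.9% to 78.7% as a span. Those are alternative outcomes, each about 3 points from 76% and well inside the CI for a cohort of 15.

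**What to change.** In section 6.6, fit one regression of log(post+0.1) on dose and log(pre+0.1) in the activity population. For each dose, take the fitted mean at the common mean of log(pre+0.1), subtract that common mean, and back-transform to give the geometric mean change with its CI. Take the dose contrasts from the same model. Keep the unadjusted log change by dose as a descriptive table, and add baseline Ki67 by dose to section 6.3. If the on-treatment Ki67 level is shown, take it from this adjusted model as supporting description, not as an unadjusted comparison of doses.

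The cost is a few lines of text and one regression on data already collected, with no new patients or samples. The downside is small: the model assumes a common log-linear slope, which is hard to verify with 15 in a cohort and can be strained by values near the +0.1 floor (a post-treatment zero from a baseline of 20 gives log(0.1/20.1) = −5.30). Check the slope across doses, and read the adjusted results alongside the unadjusted table. Because the study is open-label, the model should be written down before Ki67 results by dose are examined.

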2.4 BIOMARKER OBJECTIVE

The exploratory biomarker objective for this study is to identify and/or evaluate biomarkers that are predictive of response to GDC-9545 (i.e., predictive biomarkers), can provide evidence of GDC-9545 activity (i.e., PD biomarkers), or can increase the knowledge and understanding of disease biology and drug safety, on the basis of the following endpoints:

- Relationship between biomarkers in blood and tumor tissue (listed in Section 4.5.9) and safety, PK, activity, or other biomarker endpoints
- Cancer-related biomarkers in tumor tissue including DNA mutational status, RNA expression levels, DNA copy number and protein expression
- Modulation of ER and progesterone receptor (PR) protein levels and ER target genes through analysis of paired pre-dose and on-treatment fresh tumor biopsies

GDC-9545—Genentech, Inc.
24/Protocol GO40987, Version 4

3. STUDY DESIGN

3.1 DESCRIPTION OF THE STUDY

This is a Phase I, open-label, multicenter, preoperative study to assess changes in Ki67 levels and to evaluate the pharmacodynamics, pharmacokinetics, safety, and biologic activity of GDC-9545 in postmenopausal patients with Stage I–III operable ER-positive (HER2-negative) untreated breast cancer. Approximately 75 patients are expected to be enrolled in this study, at approximately 20–30 investigative sites globally.

The study consists of a screening period of up to 28 days; a treatment period of approximately 14 days, including a day for surgery; and a minimum follow-up period of 28 days. Patients will be assigned to one of three treatment cohorts (10, 30, and 100 mg; see [Figure 1](#)). GDC-9545 will be administered once daily up to and including the day of surgery (if allowed per local process) on Day 15 (± 2 days).

All patients will be required to provide a pretreatment tumor tissue sample. Archival tumor tissue from prior diagnostic formalin-fixed, paraffin-embedded cores (FFPE) may be used; however, if archival tissue is not available or is determined to be unsuitable for required testing, the patient will undergo a tumor biopsy. For the purpose of enrollment, ER, PR, and HER2 will be locally determined prior to beginning of study treatment. Patients who are not evaluable for the primary activity analysis as defined in [Section 6](#) will be replaced.

Surgery will take place on Day 15 (± 2). If surgery must be delayed >2 days, the Medical Monitor should be consulted. Surgery should be performed within 24 hours after the last dose of GDC-9545, if possible, to best observe PD knockdown with GDC-9545 in the surgical specimen. In lieu of surgical specimen, a biopsy on Day 14 may be obtained. The surgical specimen is not required if biopsy is obtained on Day 14.

All patients will be closely monitored for adverse events throughout the study and for at least 28 days after the final dose of study treatment (see [Section 5.3.1](#)). Adverse events will be graded according to the National Cancer Institute Common Terminology Criteria for Adverse Events, Version 5.0 (NCI CTCAE v5.0). In addition to the safety assessments conducted at scheduled clinic visits, patients will be contacted for a general assessment of adverse events at 24 hours post-surgery by telephone, if applicable.

[figure not shown]
To assess the steady-state concentrations of GDC-9545, a blood sample will be taken at surgery (see [Appendix 1](#)).

If a patient misses more than one dose or the patient's surgery is delayed beyond the allowable window, the Medical Monitor should be consulted about possible replacement.

A schedule of activities is provided in [Appendix 1](#).

GDC-9545—Genentech, Inc.
25/Protocol GO40987, Version 4

Figure 1 Sample Study Schema

QD=once a day

Note: A biopsy on Day 14 may be obtained instead of a surgical specimen. A surgical specimen on Day 15 is not required if biopsy is obtained on Day 14.

^a Post-surgery visit should be performed at Day 43 (±1 week) or prior to the initiation of another anti-cancer therapy, whichever occurs first.

